5.1 Nonclinical Experience

5.1.1 Safety Pharmacology

Safety assessments of GBT440 in three *in vivo* studies did not identify any biologically significant effects in the central nervous system (CNS) and respiratory system. There were minor effects in the cardiovascular (CV) safety pharmacology studies, with a mild increase in systolic BP at higher doses (1000 mg/kg) and a small decrease (15.3%) in hERG channel current at 10 μ M. Based on these results, there appears to be a low risk to humans for adverse effects on CNS, respiratory, or CV function.

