5.4 Risk Assessment

Based on the mechanism of action of GBT440 and findings in the nonclinical safety toxicology studies, GBT440 could cause tissue hypoxia. In GLP toxicology studies, rats dosed for 28 days with ≥ 250 mg/kg/day demonstrated increased erythropoietin and red cell mass (Hct, RBC, or Hb) with extramedullary hematopoiesis and bone marrow hypercellularity. These findings are consistent with expected physiologic compensation to hypoxia, were not considered adverse, and were reversible.

In prior clinical experience with other agents, no adverse reactions related to tissue hypoxia were reported at the highest tested doses of tucaresol administered in either healthy subjects (maximum 40% Hb-modification) or subjects with SCD (maximum 24% Hb modification), or BW12C infusions in either healthy subjects (maximum 40% Hb-modification) or subjects with SCD (23% Hb modification) ([Arya 1996](#), [Keidan 1986](#), [Nicholls 1989](#), [Rolan 1995](#)). Appropriate acute and chronic compensatory physiologic responses to tissue hypoxia were observed, including an increase in heart rate during

moderate exercise and a slight increase in reticulocyte counts at high doses ([Nicholls 1989](#), [Rolan 1995](#), [Rolan 1993](#)). Importantly, healthy subjects were well compensated- both at rest and at near maximal exercise with little change in resting heart rate ([Nicholls 1989](#)). Potential tissue hypoxia can be monitored by hematology laboratory studies, erythropoietin levels, and cardiovascular parameters.

Gastrointestinal effects (primarily emesis, and soft or liquid feces) were observed in all species and were dose-limiting in dogs and monkeys. Gastrointestinal erosions, ulcers, or epithelial hyperplasia were observed at high doses in rats.

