9.6 Clinical Safety Assessments

Assessment times are included in the schedule of events (see Section 17.0).

Vital Signs

Blood pressure, heart rate, respiration rate and oral temperature will be measured using an automated instrument after the subject has rested comfortably for 2 minutes in the supine position. Additional vital signs may be added for safety of the subjects at the discretion of the Investigator.

12 Lead ECG

Computerised 12-lead ECG recordings will be obtained as a single measurement. Each lead shall be recorded for at least 3 beats at a speed of 25 mm/sec. Subjects should be lying quietly in a fully supine position for at least 5 minutes prior to each 12-lead ECG.

The following parameters will be recorded: rhythm, ventricular rate, PR interval, QRS duration, QT and QTcF.

Medical History

A complete medical history will include evaluation (past or present) of the following: general, head and neck, eyes, ears, nose throat, chest/respiratory, heart/cardiovascular, gastrointestinal/liver, gynecological/urogenital, musculoskeletal/extremities, skin, neurological/psychiatric, endocrine/metabolic, haematologic/lymphatic, allergies/drug sensitivities, past surgeries, substance abuse or any other diseases or disorders.

Physical Examination

Physical examinations will be performed by a physician and will include the examination of the following: general appearance, eyes, ears, nose, throat, chest/respiratory, heart/cardiovascular, gastrointestinal/liver, musculoskeletal/extremities, dermatological/skin, thyroid/neck, lymph nodes, neurological/psychiatric. The physical examinations will include specific surveillance for skin rashes and lymphadenopathy.

In addition a directed physical examination may be conducted if there are any previously identified or new signs or symptoms including any adverse events or diagnoses the subject has experienced since the last visit. Changes from baseline abnormalities should be recorded at each subsequent physical examination. New or worsened abnormalities should be recorded as adverse events if appropriate.

Height and Body Weight

Height will only be measured at baseline visit. The subjects will be required to remove footwear and will wear normal indoor clothing during the measurement of height and weight.

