Day number	Last treatment day GBT440-001 (+6 days) Cohorts 15 and 17	Baseline for Cohort 7,11,12,14, 16 or 17 (within 7 days of Day 1)	a											
Dense cells	X ^h	X			X		X	X	X	X	X			X
Carboxyhaemoglobin	X ^h	X						X			X			X
HbA1c	X	X						X			X			X
NT-proBNP	X ^h	X						X			X			X
Concomitant medication diary		X	X-----											X

Key

Note: Visit 0 is the last treatment day for subjects in GBT-440-001 (Day 118 for Cohort 17 and Day 60 for Cohort 15)

- a: Enrolment and visit 1 may be combined. On admission to the clinic the subjects will be asked whether they want to be considered for study GBT440-024. If the subject is interested in being enrolled on study GBT440-024 all consent activities will be completed before the samples/procedures for GBT440-001 or GBT440-024 are collected/Performed. Visit 0 (enrolment visit) is the last day of treatment in GBT440-001, which can be 6 days before Visit 1. If the last day of treatment in GBT440-001 (Day 118 or Day 60 for Cohort 17 and Cohort 15) – the enrolment visit is not being repeated as standalone visit.
- b: Complete physical examination on enrolment, a limited physical examination on all other days. Directed physical examinations will be performed as required.
- c: 12 lead ECG (single) will be performed within 30 minutes prior to dose
- d: GBT440 900mg(three capsules) for Group 2 and GBT 440 600mg (2 capsules) for Group 4 and GBT440 900 mg (3 capsules) for Group 5 will be administered daily in the morning. On days when PK samples are drawn GBT 440 should be administered after an overnight fast.
- During the dosing period, subjects will be contacted every week in between outpatient visits to confirm GBT440 administration and subject well being.
- e: Additional samples will be collected if clinically indicated
- f: PK samples will be drawn pre dose. If the dose is increased to 1500 mg, please collect the following timepoints: pre dose, then 1-4 hours, 6-8 hours and 24 hours post dose on study visit days of Day 15 (±3 days), Day 60 (±3 days) and Days 90 (±3 days) of receiving 1500 mg.
- h: Can be omitted if measurements were collected in the past 7 days as part of the GBT440-001 study.

Table 6 Schedule of Assessments Group 3

Group 3: Subjects from Cohort 15 in the GBT440-001 study who have received GBT440 600 mg per day for 2 months will continue receiving GBT440 600 mg per day for a further 4 months (the dose may be increased if the subject tolerated 600 mg in GBT440-001).

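### On-treatment ECGs are scheduled only before the daily dose, so ECG effects near peak exposure at 1500 mg go unrecorded; the gap is probably modest and cheap to close

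*Combined protocol and SAP*

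**What the plan says.** Protocol Section 9.6 describes the method, "Computerised 12-lead ECG recordings will be obtained as a single measurement", lists what is recorded, "rhythm, ventricular rate, PR interval, QRS duration, QT and QTcF", and leaves timing to Section 17.0. There, footnote c is identical in Table 4 (Group 1), Table 5 (Groups 2, 4 and 5) and Table 6 (Group 3): "12 lead ECG (single) will be performed within 30 minutes prior to dose". No other ECG time appears.

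The PK footnote (f in the keys to Tables 4 and 5, e in the key to Table 6) starts from the same position, "PK samples will be drawn pre dose". Once a subject reaches 1500 mg it asks for samples "pre dose, then 1-4 hours, 6-8 hours and 24 hours post dose on study visit days of Day 15", and again on Days 60 and 90 of that dose. Section 8.2.1 permits titration to 1500 mg.

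Safety and tolerability are the primary objective (Section 6.1). ECG parameters are a named safety evaluation (Section 11.3) and are summarised descriptively (Section 12.5).

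**The concern.** Dosing is every morning, so an ECG in the half hour before a dose comes about 24 hours after the previous one, when concentration is lowest. An effect on QTcF or ECG ventricular rate that follows concentration would be smallest at that moment.

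This matters most at 1500 mg. Section 5.2.1 puts earlier repeated dosing in sickle cell disease at up to 1000 mg per day, given as 500 mg twice daily in Cohort 14, and 900 mg once daily in Cohort 17. The plan adds post-dose PK draws for the new dose but leaves the ECG footnote as it is for the lower doses. The report could then state that no ECG change was seen at 1500 mg when no recording was made near peak.

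**Working it through.** The plan has no QTc hypothesis, and Section 12.1 gives no statistical basis for sample size, so there is no stated figure to reproduce. Three checks apply.

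**1. Which ECGs are trough readings?** ECG rows of the schedule tables:

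- Table 4: Days 30, 60 and 88.
- Table 5: enrolment or baseline, then Days 30, 60, 90, 120, 150 and 180.
- Table 6: enrolment, then Days 30, 60, 90, 120 and 148.

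Day 88 is 88 − 60 = 28 days after the last scheduled dosing day, and Day 148 is 148 − 120 = 28 days after. These two are off-drug. So is the Group 5 baseline ECG, and the enrolment ECG of Groups 2 and 4 follows placebo. Every other scheduled ECG is pre-dose during dosing. Scheduled post-dose ECGs in the three tables: 0.

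**2. Do 1500 mg profile days meet ECG visits?** Assume the fastest titration allowed: at least 28 days at the starting dose (counting GBT440-001 for Groups 1 and 3), then 300 mg every two weeks. Study day of a profile = first day at 1500 mg + profile day − 1, matched to visits within ±3 days.

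| Group | First day at 1500 mg | Profile Day 15 | Profile Day 60 | Profile Day 90 |
|---|---|---|---|---|
| 1 | 15 | 29: Day 30 visit, ECG | 74: after dosing ends | 104: after dosing ends |
| 2, 4, 5 | 43 | 57: Day 60 visit, ECG | 102: no visit | 132: no visit |
| 3 | 29 | 43: Day 45 visit, no ECG | 88: Day 90 visit, ECG | 118: Day 120 visit, ECG |

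Each group has at least one match. If the matched ECGs move to post-dose, pre-dose ECGs on 1500 mg remain at Day 60 (Group 1), Days 90 to 180 (Groups 2, 4 and 5) and Days 30 and 60 (Group 3).

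Two limits apply. Group 4 is taken at 900 mg, as in Sections 7.1 and 8.6, but footnote d of Table 5 gives it 600 mg, and these must be reconciled. From 600 mg, 1500 mg would come at about Day 57 and the first profile at 57 + 14 = Day 71, with no visit. Also, a Group 1 subject who reaches 1500 mg only at about Day 45 has the first profile at 45 + 14 = Day 59, where the Day 60 ECG is the only one on that dose.

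**3. How far is trough from peak?** No human half-life or Tmax is given; Section 5.1.2 calls the half-life long in animals. The 1-4 and 6-8 hour windows are taken to bracket the peak. With one compartment at steady state and absorption time ignored, peak/trough = 2^(24/t½):

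- t½ = 24 h: 2.0
- t½ = 48 h: 1.41
- t½ = 72 h: 1.26

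Allowing Tmax of 1 to 8 hours, trough/peak = exp(−ln 2 × (24 − Tmax)/t½). Applied to the predicted peak of 167 µg/mL (Section 5.3.1):

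| Assumed t½ | Trough/peak | Trough, µg/mL |
|---|---|---|
| 24 h | 0.52 to 0.63 | 86 to 105 |
| 48 h | 0.72 to 0.79 | 120 to 133 |
| 72 h | 0.80 to 0.86 | 134 to 143 |

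As a sensitivity case, t½ = 12 h gives 0.27 to 0.40, or 44 to 66 µg/mL.

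**The case against.** The case for leaving the plan alone has weight:

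- Section 5.1.1 concludes that cardiovascular risk is low.
- Section 5.2.1 reports that safety committee review found no clinically significant ECG trend.
- Section 5.3.1 notes that healthy volunteers tolerated a Cmax of 294 µg/mL, which is 294/167 = 1.76 times the prediction for 1500 mg.
- With a long half-life, the trough ECG already sees most of the exposure.
- One unreplicated post-dose recording in at most 16 subjects, without a control arm, will not characterise QT.

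These points lower the importance but do not remove the gap. The protocol does not say when the GBT440-001 ECGs were taken relative to dose, so the earlier reassurance may itself rest on trough readings.

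A reader might go further and infer a QT danger near peak. Section 5.1.1 reports "a small decrease (15.3%) in hERG channel current at 10" µM. The rat figures in Section 5.1.6 (1055 µg/mL = 3127 µM) imply a molecular weight of about 337, so 167 µg/mL is about 495 µM. Dividing by (haematocrit × 150 + 1 − haematocrit) gives 14.7 µM in plasma at haematocrit 22% and 9.3 µM at 35%. The documents do not support that inference: the 150:1 ratio is animal data, the whole-blood matrix and the haematocrit are assumptions, and protein binding is not given. The comparison should carry no weight.

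Nor does the protocol name QT as an expected drug risk. QTcF and torsades risk factors appear only as exclusion criteria (Section 7.2.2), and Section 5.4 does not mention QT. Its sentence "Potential tissue hypoxia can be monitored by hematology laboratory studies, erythropoietin levels, and cardiovascular parameters" concerns hypoxia. Heart rate is also taken with vital signs, a row with no pre-dose footnote, so only the ECG ventricular rate is tied to trough.

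**Conclusion.** The point holds as a limit on what the ECG data can show. During dosing, QTcF and ECG ventricular rate are read only at trough, and nothing is recorded near peak at 1500 mg. That follows directly from the footnotes and needs no assumption beyond once-daily dosing.

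Its size does rest on assumptions. For a half-life of 1 to 3 days, the exposure left unseen is peak at about 2.0 to 1.26 times trough. A shorter half-life would widen the gap and a longer one would narrow it. The protocol's own safety evidence makes a large missed effect unlikely, so this is a modest shortfall worth correcting because correction costs little. It is not evidence that an ECG effect exists or has been missed, and no sample size or error rate changes.

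**What to change.** Amend footnote c in Tables 4, 5 and 6: where a 1500 mg PK profile day coincides with a scheduled ECG visit, record the scheduled single ECG just before the 1-4 hour PK draw. On the fastest titration these visits are Day 30 for Group 1, Day 60 for Groups 2, 4 and 5, and Days 90 and 120 for Group 3. Keep all other ECGs pre-dose.

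In Section 12.5 and the separate analysis plan:

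- Summarise post-dose ECGs separately from pre-dose ones.
- State that ECG results at other doses are trough only.
- Name the reference ECG: enrolment or baseline for Groups 2, 4 and 5; for Group 1, where Table 4 marks no enrolment ECG, the one used for the QTcF eligibility check, labelled on-treatment if taken on 900 mg; for Group 3 the enrolment ECG, labelled on-treatment at 600 mg.

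The cost is three footnote edits and a few lines of analysis text, with the same number of ECGs and no extra visit. Sections 7.1.1, 8.2 and 8.3 contain no ECG-based dosing rule, so none is affected. The downside is that a moved ECG is not time-matched to its reference, so time of day is a possible confounder, and profile days without an ECG visit stay uncovered. If the sponsor prefers an unbroken pre-dose series, one added ECG at the 1-4 hour draw would serve. Failing that, the report should say that ECGs during dosing were assessed at trough only.

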- Dose titration has been added because data from the GBT440-001 study has shown a linear and highly significant relationship between GBT440 blood level and improvement in hemolysis and no plateau effect has been reached. This suggests that subjects may derive greater benefit at higher doses achieving higher haemoglobin occupancy. Furthermore the target for optimal efficacy based on individuals with HbS/Hereditary persistence of fetal haemoglobin is 20-30% haemoglobin occupancy (Ngo 2011) and the preliminary PK data from Cohort 17 showed that the majority of subjects did not maintain haemoglobin occupancy

>20% at 900 mg daily dosing. In addition, no dose limiting toxicities or concerning dose- or exposure related toxicities pose a safety concern with higher doses. At 1500 mg, the predicted C_{max} is 167 $\mu\text{g}/\text{mL}$, which is less than the C_{max} already observed and found to be well-tolerated in healthy volunteers in GBT440-001 294 $\mu\text{g}/\text{mL}$, 900 mg [Cohort 10]). Provided the principal investigator determines that the 600 mg or the 900 mg dose is well tolerated (after at least 28 days of prior dosing), and that the subject may receive further benefit from higher dosing (further improvement in haemoglobin, reticulocyte count or unconjugated bilirubin) the dose may be increased by one capsule (300 mg) every two weeks up to a maximum of 1500 mg.

- Placebo subjects in Cohort 15 will initiate treatment with GBT440 at 900 mg to increase the likelihood of achieving haemoglobin occupancy $\geq 20\%$.
- The concomitant medication restrictions for CYP2D6 has been removed because preliminary data from the clinical drug-drug interaction study, GBT440-017, suggest that GBT440 does not inhibit metoprolol, a CYP2D6 substrate.
- The version of the SCD severity questionnaire used in this study is an older version, the updated, current version will be added to the upcoming Phase 3 study.

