Subjects from Cohort 15 in the GBT440-001 study who have received GBT440 600 mg per day for two months will continue receiving GBT440 600 mg for a further 4 months in this study or the dose may be increased if the subject has tolerated 600 mg in GBT440-001.

Group 4

Subjects from Cohort 15 in the GBT440-001 study who have received placebo for 2 months will receive GBT440 900 mg per day for 6 months in this study.

Group 5

Subjects from Cohort 7, 11, 12, 14 16 or 17 who received either GBT440 or placebo who are enrolled into this study will receive GBT440 at a dose of 900 mg per day for 6 months.

All Subjects will receive a total of 6 months treatment with GBT440 which will include treatment with GBT440 in the GBT440-001 study for subjects in Cohort 15 or 17. Subjects from Cohort 7, 11, 12, 14, 16 or 17 who received either GBT440 or placebo and are currently off study in GBT440-001 will receive a total of 6 months of treatment with GBT440 in this study..

The dose may be increased by 300 mg increments (1 capsule) every 2 weeks up to maximum of 1500 mg, if in the opinion of the investigator the subject is tolerating the current dose level and might derive further benefit from an increase in dose (e.g. hemolysis measures have improved but not normalized).

A Safety Monitoring Committee (SMC) consisting of the Principal Investigator, Sponsor Medical Monitor, and Independent Safety Physician will have overall responsibility for assessing safety and tolerability. The SMC will review cumulative data at least monthly to determine whether continued dosing may proceed. The responsibilities of the SMC will be described in a separate charter.

Number of Subjects:

Up to 8 SCD subjects from GBT440-001 cohort 17 (900 mg per day), up to 8 SCD subjects from GBT440-001 cohort 15 (600 mg per day), and additional SCD subjects who previously completed GBT440-001 may be enrolled up to a total sample size not exceeding 16 subjects.

Main Criteria for Inclusion:

Subjects with SCD who are currently enrolled in the GBT440-001 study, Cohort 15 or 17.

Subjects with SCD from Cohort 7, 11, 12, 14, 16 or 17 from the GBT440-001 study.

Eligibility may be determined from assessments obtained as part of the GBT440-001 study within 7 days of dosing in this study for subjects in Cohort 15 or 17.

Eligibility must be determined from assessments obtained during baseline visit for subjects who were previously enrolled in Cohorts 7, 11, 12, 14, 16 or 17.

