5.3.1 Rationale for Dose Titration

Dose titration has been added because data from the GBT440-001 study has shown a linear and highly significant relationship between GBT440 blood level and improvement in hemolysis and no plateau effect has been reached. This suggests that subjects may derive greater benefit at higher doses achieving higher haemoglobin occupancy. Furthermore the target for optimal efficacy based on individuals with HbS/Hereditary persistence of fetal haemoglobin is 20-30% haemoglobin occupancy (Ngo 2011) and the preliminary PK data from Cohort 17 showed that the majority of subjects did not maintain haemoglobin occupancy >20% at 900 mg daily dosing. In addition, no dose limiting toxicities or concerning dose-or exposure related toxicities pose a safety concern with higher doses. Doses of 1000 mg for 28 days and 900 mg for 90 days have been well tolerated, with the majority of AEs were Grade 1 or 2 in severity. At 1500 mg, the predicted C_{max} is 167 μ g/mL, which is less than the C_{max} already observed and found to be well-tolerated in healthy volunteers in GBT440-001 (294 μ g/mL at 900 mg [Cohort 10]).

To assess the higher dose of 1500 mg, subjects will be dose escalated by 300 mg over 2-week intervals. The principal investigator will determine if the 600 mg or the 900 mg dose is well tolerated (after at least 28 days of prior dosing), and that the subject may receive further benefit from higher dosing (further improvement in haemoglobin, reticulocyte count or unconjugated bilirubin) the dose may be increased by one capsule (300 mg) every two weeks up to a maximum of 1500 mg.

This study will be performed in compliance with the protocol, ICH GCP and applicable regulatory requirements. Aspects of the study concerned with the investigational medicinal product(s) (IMPs) will meet the requirements of EU GMP.

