8.2.1 Dose Titration

Provided the Principal Investigator determines that the 600mg dose (in Cohort 15), 900 mg dose (in Cohort 17), and 900 mg dose in the Cohorts 7, 11, 12, 14, 16 or 17 is well tolerated (after at least 28 days of dosing), and that the subject may receive further benefit from higher dosing (further improvement in haemoglobin, reticulocyte count or unconjugated bilirubin) the dose may be increased by one capsule (300 mg) every two weeks up to a maximum of 1500 mg dose.

When increasing the dose, the subject should return to clinical every 2 weeks for Laboratory and AE assessments

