8.6 Method of Assigning Subjects to Treatment Groups

Following confirmation of continued eligibility subjects will be assigned to the following treatment groups:

Group 1

Subjects from Cohort 17 in the GBT440-001 study who have received GBT440 900 mg per day for 4 months will continue receiving GBT440 900 mg per day for a further 2 months in this study.

Group 2

Subjects from Cohort 17 in the GBT440-001 study who have received placebo for 4 months will receive GBT440 900 mg per day for 6 months in this study.

Group 3

Subjects from Cohort 15 in the GBT440-001 study who have received GBT440 600 mg per day for 2 months will continue receiving GBT440 600 mg for a further 4 months in this study or the dose may be increased if the subject has tolerated 600 mg in GBT440-001.

Group 4

Subjects from Cohort 15 in the GBT440-001 study who have received placebo for 2 months will receive GBT440 900mg per day for 6 months in this study.

Group 5

Subjects from Cohort 7, 11, 12, 14, 16 or 17 who received either GBT440 or placebo who are enrolled into this study will receive GBT440 at a dose of 900 mg per day for a total of 6 months in this study.

All Subjects will receive a total of 6 months treatment with GBT440 which will include treatment with GBT440 in the GBT440-001 study for subjects in Cohort 15 or 17.

Subjects from Cohort 7, 11, 12, 14, 16 or 17 who received either GBT440 or placebo will receive a total of 6 months of treatment with GBT440 in this study.

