- f: PK samples will be drawn pre dose. If the dose is increased to 1500 mg, please collect the following timepoints: pre dose, then 1-4 hours, 6-8 hours and 24 hours post dose on study visit days of Day 15 (± 3 days), Day 60 (± 3 days) and Days 90 (± 3 days) of receiving 1500 mg.g: Days 15 and 45 are only to be conducted if the dose is increased to 1500 mg.
- h: Can be omitted if measurements were collected in the past 7 days as part of the GBT440-001 study.

Table 5 Schedule of Assessments for Groups 2, 4 and 5

Groups 2: Subjects from Cohort 17 in the GBT440-001 study who have received placebo for 4 months will receive GBT440 900mg per day for 6 months

Group 4: Subjects from Cohort 15 in the GBT440-001 study who have received placebo for 2 months will receive GBT440 900 mg per day for 6 months

Group 5: Subjects with SCD from Cohorts 7, 11, 12, 14, 16 or 17 in the GBT440-001 study will receive GBT440 900 mg per day for 6 months

Assessments	Enrolment a	Baseline for Cohort 7,11,12,14, 16 or 17 (within 7 days of Day 1)	Outpatient Treatment Period											
			1 +/-3 days a	15 +/-3 days	30 +/-3 days	45 +/-3 days	60 +/-3 days	90 +/-3 days	120+/-3 days	150+/-3 days	180 +/-3 days	187+/-3 days	194 +/-5 days	208 End
Day number	Last treatment day GBT440-001 (+6 days) Cohorts 15 and 17													
Visit number	0		1	2	3	4	5	6	7	8	9	10	11	12
Informed consent	X	X												
Eligibility assessment	X	X												
Medical History	X	X												
Physical examination b	X	X		X	X		X	X	X	X	X			X
Weight	X	X		X	X	X	X	X	X	X	X			X
Vital signs	X	X	X	X	X	X	X	X	X	X	X			X
12 Lead ECG (single) c	X	X			X		X	X	X	X	X			
Drug administration d				X-----							X			
Adverse events				X-----										X
Urinalysis e	X	X						X	X	X	X			X
Urine microalbumin/creatinine	X	X						X			X			
Haematology e	X	X		X	X	X	-	X	X	X	X			X
Serum biochemistry e	X	X		X	X	X	X	X	X	X	X			X
Coagulation e	X	X		X		X		X	X	X	X			X
Pregnancy test (females only)	X	X			X		X	X	X	X	X			X
Haemoglobin electrophoresis		X						X			X			X
PK samples (plasma and whole blood) f	X			X	X		X	X	X	X	X	X	X	X
Serum erythropoietin	X ^h	X			X		X	X	X	X	X			X
Exploratory plasma biomarkers	X ^h	X			X		X	X	X	X	X			X

Assessments	Enrolment a		Outpatient Treatment Period											
			1 +/-3 days	15 +/-3 days	30 +/-3 days	45 +/-3 days	60 +/-3 days	90 +/-3 days	120+/-3 days	150+/-3 days	180 +/-3 days	187+/-3 days	194 +/-5 days	208 End

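### Table 5 footnote d tells staff to give Group 4 600 mg (2 capsules), but the protocol assigns that group 900 mg (3 capsules) everywhere else

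*Combined protocol and SAP*

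**What the plan says.** Footnote d in the key to Table 5 (Section 17.0) sets the daily dose for the three groups sharing that schedule. Groups 2 and 5 are given 900 mg as three capsules. For the remaining group the instruction is "GBT 440 600mg (2 capsules) for Group 4".

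Four other places state the Group 4 dose:

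- Table 5 heading: "Group 4: Subjects from Cohort 15 in the GBT440-001 study who have received placebo for 2 months will receive GBT440 900 mg per day".
- Synopsis, Section 3.0: "Subjects from Cohort 15 in the GBT440-001 study who have received placebo for 2 months will receive GBT440 900 mg per day".
- Section 7.1: the same assignment, 900 mg per day.
- Section 8.6, which allocates subjects to groups: "Subjects from Cohort 15 in the GBT440-001 study who have received placebo for 2 months will receive GBT440 900mg per day".

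The rationale for revisions at the front of the protocol gives the reason: "Placebo subjects in Cohort 15 will initiate treatment with GBT440 at 900 mg to increase the likelihood of achieving haemoglobin occupancy" of at least 20%.

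On later increases, the synopsis says "The dose may be increased by 300 mg increments (1 capsule) every 2 weeks up to maximum of 1500 mg", with no minimum time at the starting dose. Section 5.3.1 has the investigator judge "if the 600 mg or the 900 mg dose is well tolerated (after at least 28 days of prior dosing") before any increase. Section 8.2.1 also requires 28 days, but names the starting doses by cohort: "the 600mg dose (in Cohort 15), 900 mg dose (in Cohort 17").

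**The concern.** Table 5 contradicts its own heading on the dose of study drug for one group. The footnote belongs to the row that governs dosing, so site staff could reasonably work from it. Section 8.2, on dosage and administration, gives no starting dose by group. That leaves footnote d as the only place in the protocol that converts the Group 4 dose into a daily number of capsules. Section 15.2 requires exact adherence to the protocol's instructions, and for Group 4 that cannot be done, because either dose departs from some part of the text.

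What is at stake is a starting dose below the one assigned. This amendment chose 900 mg deliberately, to improve the chance of reaching the occupancy target. Section 5.3.1 reports that most Cohort 17 subjects did not hold occupancy above 20% even at 900 mg, so a lower start works against the stated purpose.

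**Working it through.** **1. Is the footnote consistent within itself?** Capsules = daily dose / capsule strength. Section 8.1 gives a strength of 300 mg. For the footnote, 600 / 300 = 2, which matches its own count. Dose and count agree, so this is not a stray digit or an extraction fault.

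**2. Does it follow from the assigned dose?** 900 / 300 = 3 capsules, the count the same footnote gives Groups 2 and 5. It does not give 2.

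**3. Statements of the Group 4 dose side by side**

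| Place | Group 4 daily dose |
|---|---|
| Synopsis, Section 3.0 | 900 mg |
| Section 7.1 | 900 mg |
| Section 8.6 | 900 mg |
| Table 5 heading | 900 mg |
| Table 5 footnote d | 600 mg (2 capsules) |

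All five are current text. The amendment summary and rationale also give 900 mg and serve only as corroboration.

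**4. Does anything else support 600 mg?** Two passages link Cohort 15 with 600 mg: the number of subjects in the synopsis, and Section 8.2.1. Both fit the parent-study dose or Group 3, which continues on 600 mg. Neither assigns 600 mg to Group 4.

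**5. Size of the dose error.** 900 − 600 = 300 mg per day; 300 / 900 = 33%.

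**6. Earliest possible 1500 mg dose, in days after starting**

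| Titration rule | Start at 900 mg | Start at 600 mg | Delay |
|---|---|---|---|
| Sections 5.3.1 and 8.2.1: 28 days, then +300 mg every 14 days | 1200 at 28, 1500 at 42 | 900 at 28, 1200 at 42, 1500 at 56 | 56 − 42 = 14 |
| Synopsis: +300 mg every 14 days, no 28-day minimum | 1200 at 14, 1500 at 28 | 900 at 14, 1200 at 28, 1500 at 42 | 42 − 28 = 14 |

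**7. Subjects affected.** Section 5.2.1 gives no active-to-placebo split for Cohort 15. Cohorts 7, 14 and 16, each of eight subjects with SCD, were split 6 to 2. Assuming the same for Cohort 15, and since participation is optional (Section 7.1), Group 4 is 0, 1 or 2 subjects. Out of the maximum of 16 that is 0%, 6.25% or 12.5%. The only enrolments reported, as of 03 August 2016, were two Cohort 17 subjects.

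**The case against.** The contradiction itself cannot be answered; what can be argued is its weight.

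- **Clear intent.** 900 mg is stated four times in the body, including the section that assigns groups and the heading a reader meets before the footnote. 600 mg is also a permitted dose in this study, used in Group 3, and the investigator may increase it. Pharmacy handling is covered by a separate manual (Section 8.1.1). This limits the likely harm, but the manual is not available here and cannot be assumed to correct the footnote.
- **The delay is hypothetical.** Titration is at the investigator's discretion and no subject is assigned to reach 1500 mg. Nor is 14 days the only possible figure. If Section 5.3.1 is read as requiring 28 days at 900 mg as well as at 600 mg, a 600 mg start reaches 900 at day 28, 1200 at day 56 and 1500 at day 70. That is 70 − 42 = 28 days late. The delay is therefore illustrative; the finding does not depend on it.
- **The headcount is assumed.** This stands. One Cohort 15 subject is reported as dosed for 28 days, whereas Group 4 is defined by two months on placebo, so the eligible pool may be seven rather than eight.
- **Section 8.2.1 is only loosely worded.** Also fair. The synopsis and Section 5.3.1 set no cohort limit and already cover a 900 mg start, so no rule is missing.

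**Conclusion.** The concern holds. Footnote d is wrong as written: Group 4 should receive 900 mg, or 3 capsules, daily. This rests on direct comparison of current text and needs no assumption. Following the footnote would start Group 4 subjects 300 mg per day (33%) too low, against the protocol's stated reason for the 900 mg start.

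The consequences are limited. The estimate of 0 to 2 subjects depends on an assumed 6-to-2 split, and nothing shows that any Group 4 subject was dosed from the footnote. The error is towards a lower dose, so no added toxicity is claimed. The documents give no occupancy data at 600 mg for Cohort 15, so no loss of efficacy can be quantified. No effect on the planned descriptive analyses is claimed. The point should be fixed because it is a dosing instruction, but it does not threaten the study's conclusions.

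**What to change.** In Table 5 footnote d, change the Group 4 entry to GBT440 900 mg (3 capsules).

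Optionally, in the same edit, limit the 600 mg reference for Cohort 15 in Section 8.2.1 to Group 3 and name 900 mg as the starting dose for Group 4.

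The cost is one footnote and, if wanted, one clause, issued in an amendment or clarification letter. Design, visits, sample size and analysis are unchanged.
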